2.2.2.1.3 Safety Pharmacology

The effect of HMPL-306 on hERG potassium channels was evaluated using HEK293 cell line. The half-maximal inhibitory concentration of HMPL-306 was CCI μ M on hERG potassium channels, CCI.

CCI in unrestrained and telemetered Beagle dogs at single doses up to CCI mg/kg, the highest dose employed, further supporting a low risk of HMPL-306 on the cardiovascular system.

Single doses up to CCI mg/kg, the highest dose used, were administered via oral gavage to Sprague-Dawley rats. CCI.

Collectively, the results of the safety pharmacology studies indicate that HMPL-306 is low risk to the cardiovascular, respiratory, and central nervous system.

2.2.2.2 Pharmacokinetics

HMPL-306 has good in vitro permeability and is not a substrate of efflux transporters. Clearance of HMPL-306 in rats and dogs was CCI CCI.

HMPL-306 is stably metabolized in in vitro CCI in various species, and the major in vitro metabolite observed was the CCI. In vitro glucuronyl transferase study results showed that CCI.

CCl were the main metabolic enzymes that mediate the generation of glucuronic acid conjugate.

In vitro studies showed that HMPL-306 exhibits a relatively CCI.

HMPL-306 showed relatively CCI.

HMPL-306 has an CCI.

CCI [REDACTED] . HMPL-306
CCI [REDACTED] . HMPL-306 is CCI [REDACTED]
[REDACTED]

2.2.2.3 Toxicology

The completed HMPL-306 toxicology studies included single-dose toxicity studies in rats and dogs, 4-week repeat-dose toxicity studies with an 8-week recovery period in rats and dogs, genotoxicity studies (bacterial reverse mutation test, in vitro chromosomal aberration test, and an in vivo micronucleus test), and a phototoxicity study in rats. The results showed that single-dose administrations of HMPL-306 in rats and dogs were CCI [REDACTED] with maximum tolerated doses of CCI [REDACTED] mg/kg and CCI [REDACTED] mg/kg, respectively.

In the 4-week repeat-dose toxicity studies of rats and dogs, CCI [REDACTED] was observed in either of the 2 species. In the rats, CCI [REDACTED]
[REDACTED] were observed. There were CCI [REDACTED] observed in the dogs. The common target organ was CCI [REDACTED]
[REDACTED]. Changes in the CCI [REDACTED] were also observed at the high dose of rats at the end of the dosing period. After the 8-week recovery period, CCI [REDACTED] was still observed in the high-dose female rats, and all of the other aforementioned changes recovered.

HMPL-306 was not CCI [REDACTED].

Further details on pharmacology, pharmacokinetics, and toxicology are provided in the Investigator's Brochure (IB).

2.2.3 Supportive Clinical Data

A phase 1 study is currently ongoing in China to evaluate safety, tolerability, and preliminary anti-tumor activity of HMPL-306 in patients with advanced hematological malignancies that harbor mIDH1/2 (NCT04272957). Refer to the latest HMPL-306 IB for the most updated clinical data summary.

2.3 Benefit/Risk Assessment

2.3.1 Benefit-Risk Assessment

The patients to be enrolled in this study will be those with advanced, relapsed, refractory, or resistant hematological malignancies and, therefore, have an unmet medical need.

For patients with refractory AML, the median overall survival (OS) is approximately 1.5 months with only 8% one-year survival (Gale 2008, Giles 2005). National Comprehensive Cancer Network (NCCN) and European Society for Medical Oncology (ESMO) practice guidelines recommend considering clinical trial for patients with primary refractory AML (NCCN-AML 2021, Heuser 2020). In the event that no clinical trial is available, then the intent of a second salvage chemotherapy in these patients, however, is only supportive at best. Therefore, patients with AML who have received at least 2 prior lines of therapy do not have a viable

treatment option available. Additionally, AML patients who fail IDH inhibitor therapies do not have any standard treatment options available, making them a population with very high unmet need ([NCCN-AML 2021](#)).

High-risk MDS (HR-MDS) carries a major risk of progression to AML and short survival. There are no standard treatment options for patients with relapsed or refractory HR-MDS. Patients ineligible for allo-HSCT have no approved second-line treatment options after failure of an approved hypomethylating agent (HMA), and clinical trials are the recommended option as per NCCN and ESMO guidelines ([NCCN-MDS 2021](#), [ELN 2017](#), [Fenaux 2020](#)).

Similarly, ESMO and NCCN practice guidelines recommend considering clinical trial for patients with relapsed or refractory AITL because of the poor survival rate with available single agent palliative therapy options ([NCCN-MDS 2021](#), [NCCN-PTCL 2021](#), [d'Amore 2015](#)).

HMPL-306 is a dual inhibitor of IDH1 and IDH2, which, in preclinical studies, has demonstrated similar efficacy to single target IDH inhibitors (ivosidenib and enasidenib), and may have similar benefit to other IDH1 and/or IDH2 inhibitors in the same class. Preclinical studies, including toxicology studies, indicate that HMPL-306 is well tolerated. Additionally, there are no approved therapies for the treatment of hematological malignancies that have been previously treated with an mIDH1 or mIDH2 inhibitor, thus providing a potential treatment option in an area of unmet medical need.

Most toxicities associated with the use of FDA-approved IDH1 and IDH2 inhibitors are considered to be mild and are well managed. Incidence of Grade 3 and Grade 4 events have been observed to occur at a lower frequency with these agents compared to other available treatments for AML. The most common toxicities associated with IDH1 and IDH2 inhibitors include differentiation syndrome, tumor lysis syndrome, hyperbilirubinemia, anemia, febrile neutropenia, thrombocytopenia, fatigue, nausea, and diarrhea ([Stein 2017](#), [DiNardo 2018](#)). The incidence rate and severity of toxicities in these FDA approved IDH1 and IDH2 inhibitors is consistent with the safety profile of HMPL-306 in patients with hematologic malignancies. Further details on identified and potential risks of HMPL-306 are provided in the Investigator's Brochure (IB).

Taking into account the measures taken to minimize risk to patients in this study as defined in Section [7.4](#), Section [7.5](#), Section [7.6](#), and [Appendix 11](#), the risks identified in association with HMPL-306 are justified by the anticipated benefits that may be afforded to patients with solid tumors with IDH mutations as defined in Section [5.2](#).

In summary, patients with AML who have received at least 2 prior lines of therapy including IDH inhibitors and patients with AITL and HR-MDS who have received at least 1 prior line of therapy do not have viable treatment options. This study provides an opportunity for these patients to participate in a study of HMPL-306, a novel agent that targets mutations that are common among these tumors. Thus, HMPL-306 can potentially provide clinical benefit to patients with advanced, relapsed, refractory, or resistant hematological malignancies.

Refer to the latest HMPL-306 IB for the most updated clinical and safety data.

3 OBJECTIVES AND ENDPOINTS

The objectives and corresponding endpoints are summarized in [Table 3](#).

Table 3 Objectives and Corresponding Endpoints

Tier	Objectives	Endpoints
Primary	Part 1: To evaluate the safety and tolerability of HMPL-306 in patients with advanced hematological malignancies that harbor IDH mutations	MTD and/or RP2D Safety, including DLTs, TEAEs, SAEs, deaths, ECGs, and clinical laboratory abnormalities
	Part 2: To characterize safety and tolerability, and to determine RP2D of HMPL-306 in patients with advanced hematological malignancies that harbor IDH mutations	Safety including DLTs, TEAEs, SAEs, deaths, ECGs, and clinical laboratory abnormalities
Secondary	To assess preliminary antitumor activity of HMPL-306 in patients with advanced hematological malignancies that harbor IDH mutations	Best overall response, ORR, TTR, DoR, CBR, PFS, OS, DFS, EFS, and postbaseline transfusion independence
	To assess the PK of HMPL-306 in patients with advanced hematological malignancies that harbor IDH mutations	Observed plasma concentrations and exposure parameters of HMPL-306
	To assess PD of HMPL-306 in patients with advanced hematological malignancies that harbor IDH mutations	Observed plasma concentrations of 2-HG
Exploratory	To explore relationships between changes in frequency of genetic mutation, efficacy, PK, PD, and safety after HMPL-306 treatment	Changes from baseline in tumor markers, correlation with drug exposure, target engagement, and efficacy and safety outcomes
	To explore relationships between HMPL-306 PK exposure, TE, 2-HG levels, and percent inhibition	
	To explore the influence of genetic abnormalities other than IDH mutations on safety, efficacy, PD and PK, and clinical response to HMPL-306 treatment	

2-HG=2-hydroxyglutaric acid; CBR=clinical benefit rate; DFS=disease-free survival; DLT=dose-limiting toxicity; DoR=duration of response; ECG=electrocardiogram; EFS=event-free survival; IDH=isocitrate dehydrogenase; MTD=maximum tolerated dose; ORR=objective response rate; OS=overall survival; PK=pharmacokinetics; PD=pharmacodynamics; PFS=progression-free survival; PR=partial response; RP2D=recommended phase 2 dose; SAE=serious adverse event; SD=stable disease; TE=target engagement; TEAE=treatment-emergent adverse event; TTR=time to response.

4 STUDY PLAN

4.1 Study Design

This is a phase 1, open-label, multicenter, single-arm study to evaluate safety, tolerability, PK, PD, and preliminary efficacy of HMPL-306 administered orally in treatment of patients with advanced relapsed, refractory, or resistant hematological malignancies that harbor IDH mutations.

The study consists of 2 parts: dose escalation part (Part 1) and dose expansion part (Part 2).

4.1.1 Part 1 (Dose Escalation)

The first part of the study is dose escalation, where cohorts of patients will receive ascending oral doses of HMPL-306 to determine MTD and/or the recommended phase 2 dose (RP2D). The modified toxicity probability interval-2 (mTPI-2) ([Greenberg 2012](#), [Guo 2017](#)) design will be used to perform dose escalation and MTD/RP2D determination. Briefly, the mTPI-2 method uses a Bayesian framework and a hierarchical model to compute the dose escalation based on the interval between the toxicity rate of each dose level and target probability ([Greenberg 2012](#), [Guo 2017](#)). This study is designed targeting a dose-limiting toxicity (DLT) rate of 20% with an equivalence interval of 15% to 25%.

Like the 3+3 design, the mTPI-2 method incorporates prespecified escalation rules that can be presented in a table ([Table 5](#)). As shown in [Table 5](#), the number of patients dosed at a given dose level are shown in the columns, while the rows indicate the number of DLTs experienced. The escalation/de-escalation rules from the table will be used for each dose level evaluated; the patient numbers and DLTs do not carry over from cohort to cohort. As an example, within a cohort:

- If none of the 3 patients experience a DLT → escalate the dose (“E” at column 3 row 0) to the next dose level cohort.
- If 1 out of 3 patients experience a DLT → de-escalate to a lower dose level (“D” at column 3 row 1).
- If 2 out of 3 patients experience a DLT → the dose is determined to be unacceptably toxic and will not be used again, de-escalate to a lower dose level (“DU” at column 3 row 2).
- If 1 out of 5 patients experience a DLT → stay at the same dose level (“S” at column 5 row 1).

The following rules apply during dose escalation:

- Starting dose at Cohort 1 is **100** mg.
- Although in the mTPI-2 method the cohort size is not fixed, at least 3 patients will be enrolled at each dose level. When all patients at a dose level complete DLT assessment, the study will escalate to the next dose level and another minimum of 3 patients will be recruited in this order until RP2D or MTD ([Table 5](#)).
- The sample size of a dose cohort that has already passed the preliminary DLT assessment (3 to 6 patients) and shown efficacy (eg, to include other efficacy signal for each tumor type) can be extended to 12 patients in order to further evaluate the safety and efficacy signals of that particular dose.

- If agreed upon by the investigators and the sponsor (eg, based on safety, PK, exposure, and TE and/or PD data from prior and current cohorts) that increasing the dose further may not yield additional benefit, the dose may stay at the current dose level, be de-escalated to any dose, or no future escalation may be made, even if the rule indicates “E” to escalate.
- Before MTD is reached, if PK evidence suggests the dose-exposure and TE relationship is saturated, dose escalation may be discontinued.
- The need for dose escalation to a specific dose beyond **CCI** mg QD or de-escalation to an intermediate dose level will be evaluated jointly by investigators and the sponsor based on cumulative clinical safety, PK, and preliminary efficacy data.

The stopping rules for this portion of the study are defined in Section [6.2.2](#).

PK week: The PK week is defined as 7 days prior to cycle 1 day 1 (C1D1), during which a single dose of HMPL-306 will be administered on Day 1 of PK week (Day - 7 relative to C1D1). Serial blood samples will be collected from Days 1 to 7 of the PK week for analysis of plasma concentrations of HMPL-306, 2-HG, and other biological markers as defined by the sponsor.

Study treatment: One cycle of study treatment is defined as 28 days of continuous, daily dosing. After the PK week, dose escalation will start at **CCI** mg QD orally (PO) for Cohort 1 and then escalate in the sequence of **CCI** mg QD, and **CCI** mg QD (see [Table 4](#)). The modified Fibonacci sequence will be used to increment the dose (see [Table 5](#) for details on the dose escalation decision).

No DLTs or safety concerns were noted in dose levels 1 to 3. Based on the collective results of the preclinical in vitro and in vivo safety pharmacology, at a clinical dose of **CCI** mg, the risk for potential effects on the cardiovascular, respiratory, and central nervous systems is considered low after administration of HMPL-306. The anticipated human exposure (as determined by area under the curve [AUC]) at a clinical dose of **CCI** mg QD did not result in severe toxic findings in the 4-week toxicology studies and is expected to be well below the exposures at the highest doses studied. Please refer to the most recent IB for additional information.

Safety monitoring and evaluation of each dose escalation cohort will be carried out by the Safety Review Committee (SRC), which is comprised of the sponsor and investigators. The enrollment of dose levels 5 to 8 will be based on the cumulative safety and preliminary PK and PD data observed at **CCI** mg, and review will be conducted by the sponsor and the SRC members.

Table 4 Patient Dose Grouping, Dose Escalation Plan

Cohort #/Dose Level	Dose of HMPL-306 (PO QD with Water)
1	cc1 mg
2	CC1 mg
3	mg
4	mg
5	mg
6	mg
7	mg
8	mg

PO=orally, QD=once daily.

Note: Patients in dose escalation will receive 1 single-dose of HMPL-306 7 days prior to C1D1.

Table 5 mTPI-2 Decision Table for Dose Selection

Target toxicity probability: pT=20%; $\epsilon_1=0.05$; $\epsilon_2=0.05$

		Number of Patients in a Cohort											
		1	2	3	4	5	6	7	8	9	10	11	12
Number of Patients with a DLT	0	E	E	E	E	E	E	E	E	E	E	E	E
	1	D	D	D	D	S	S	S	E	E	E	E	E
	2		DU	DU	D	D	D	D	S	S	S	S	S
	3			DU	DU	DU	DU	D	D	D	D	D	D
	4				DU	DU	DU	DU	DU	DU	D	D	D
	5					DU							
	6						DU						
	7							DU	DU	DU	DU	DU	DU
	8								DU	DU	DU	DU	DU
	9									DU	DU	DU	DU
	10										DU	DU	DU
	11											DU	DU
	12												DU

E=escalate to the next higher dose; S=stay at the same dose; D=De-escalate to the previous lower dose; DLT=dose-limiting toxicity; DU=De-escalate to the previous lower dose and the current dose will not be used again in this study; MTD=maximum tolerated dose.

Note: The horizontal axis indicates the number of patients who are treated at the current dose and the longitudinal axis is the number of observed dose-limiting toxicities. ϵ_1 and ϵ_2 are fractions used to define an equivalence interval of MTD.

Safety Review Committee

Safety monitoring and evaluation of dose escalation will be carried out by the Safety Review Committee (SRC), which is comprised of the sponsor and investigators. The SRC will determine whether it is safe to continue to next predefined higher dose level, stay at the currently assigned dose level or whether the dose should be de-escalated to any lower dose, and finally, to determine RP2D based on evaluation of safety, PK, and PD data. The SRC, on an ongoing basis, will also monitor the benefit-risk of HMPL-306 treatment in the expansion cohort and make recommendations on the continuation of enrollment in the study.

Dose-Limiting Toxicity

DLT is defined as occurrence of any treatment-emergent adverse event (TEAE) as described in Section 8.1.3 during the DLT assessment window, unless clearly unrelated to the study drug as per investigator's discretion.

DLT Assessment Window:

For all patients in dose escalation, DLTs will be assessed during the DLT assessment window. This is the first 28 days of continuous study treatment (C1D1 through C1D28), and does not include the dose administered during PK week.

DLT-Evaluable Patient:

A patient is DLT-evaluable if the following criteria are met:

- has received at least 75% of the assigned dose of study drug during the DLT assessment window

OR

- has not completed DLT assessment period due to a DLT

For decisions on dose escalation, each dose cohort shall present the protocol-required numbers of DLT-evaluable patients. Patients who are not DLT-evaluable in a dose cohort may be replaced to guarantee the protocol-required number of DLT-evaluable patients for dose escalation evaluations.

Patients who complete the DLT assessment window will be allowed to continue treatment until disease progression, intolerable toxicity, withdrawal of consent, lost to follow-up, end of study, conditions are met per Section 6.2.1, or death, whichever comes first.

Maximum Tolerated Dose

The MTD determination will be driven by the mTPI-2 method. The MTD will be any doses with true toxicity probability in the equivalence interval. For this study, the equivalence interval is defined as 15% to 25%.

Recommended Dose of the Expansion Cohort and Phase 2 Clinical Study (RP2D)

RP2D determination will take the following criteria under consideration:

- Determination of MTD achieved during the dose escalation part
- Assessment of safety, PK, and PD

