6.2.2.2 Stopping Rules for a Cohort or the Study

Dose Escalation Part

The stopping rules at a cohort level are based on mTPI-2 method and defined in [Table 5](#). There will be no escalation to the next higher dose level cohort, until all available data from the current dose level cohort have been reviewed by SRC, who will then recommend appropriate dose escalation, de-escalation, or discontinuation.

This dose escalation part will be suspended, interrupted, or discontinued before MTD is attained based on:

1. Recommendation of SRC, and/or
2. Results of the analysis of emerging PK data suggesting that drug exposure or TE is saturated.

[figure not shown]
The dose escalation part of the study will prematurely end when any of the following conditions are met:

1. Excessive toxicity is present in the initial dose, ie, if DLT is observed in 1 out of 3 patients at the first dose level. If this occurs at the initial dose level, data will be reviewed by the SRC to determine next steps for the study.
2. Although no excessive toxicity is present in the first dose level cohort, if the dose returns to the initial dose according to the rules in [Table 5](#) and excessive toxicity is present at the initial dose (for example, 2 or more patients with a DLT are observed in 6 patients).

Dose Expansion Part:

This part utilizes MTD or RP2D that has been determined as safe by SRC based on the conclusion of dose escalation part. The sponsor will periodically review evolving aggregate safety data by appropriate methods.

CCI

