9.1.2.1 Dose Escalation Part

The maximum sample size in this part will be determined jointly by the sponsor and investigator. The exact sample size of mTPI-2 design in dose escalation part cannot be prespecified due to dynamic nature of Bayesian allocation procedure. Patients not evaluable for DLT may be replaced, and this may result in the number of patients enrolled being more than expected. An estimated 24 to 30 evaluable patients may be enrolled in this part.

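### Table 5 prints Stay at 2 DLTs in 8 patients, where mTPI-2 at the stated target and interval, with an assumed uniform prior, gives De-escalate

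*Protocol*

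**What the plan says.** Protocol section 4.1.1 names mTPI-2 as the escalation method and sets a target DLT "rate of 20% with an equivalence interval of 15% to 25" per cent. Table 5, "mTPI-2 Decision Table for Dose Selection", repeats these settings as pT = 20% with both epsilons at 0.05. Its row for 2 DLTs, starting at 2 patients, reads "DU DU D D D D S S S S S", so the entry for 8 patients is S (stay at the same dose). The section's worked example for 2 DLTs in 3 patients (DU) falls in the right column, so the row is correctly aligned.

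The table also serves as the stopping rule. Section 6.2.2.2 says: "The stopping rules at a cohort level are based on mTPI-2 method and defined in" Table 5. Section 4.1.1 adds that mTPI-2 drives the choice of MTD, and MTD and/or RP2D is a Part 1 primary endpoint.

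A cohort can reach 8 patients because a dose that has passed its preliminary DLT assessment and shown efficacy "can be extended to 12 patients in order to further evaluate the safety and efficacy signals". Neither the prior nor the sub-interval widths nor the cutoff for DU is given in the protocol or SAP.

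**The concern.** Three cells in the tested rows have an observed DLT rate of exactly 25%, the upper edge of the equivalence interval: 1/4, 2/8 and 3/12. Table 5 prints D, S and D. That pattern is odd on its face, and it prompts the question whether one set of mTPI-2 settings could produce it.

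If 2/8 is the wrong cell, the operative escalation and stopping table has one threshold set too permissively, and a dose could be kept where the named method would step down. If 1/4 is the wrong cell instead, the printed D there is stricter than the method.

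**Working it through.** **Inputs from the protocol (4.1.1, Table 5).** pT = 0.20; epsilons 0.05 and 0.05; equivalence interval 0.15-0.25; the printed decisions in rows 0 to 4 (54 cells). Rows 5 and above were not compared, because the text extracted from the PDF is broken there.

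**Assumptions, not in the documents.** Beta(1,1) prior; sub-intervals 0-0.05, 0.05-0.15, 0.15-0.25 (Stay), 0.25-0.35, and so on to 0.95-1. The decision follows the interval with the highest unit probability mass (UPM). DU is counted as D.

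**Formula.** With x DLTs in n patients the posterior is Beta(1+x, 1+n-x), and UPM = posterior probability of the interval / its width.

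**The cell 2/8.** The posterior is Beta(3,7). Its distribution function is 0.14085 at 0.15, 0.39932 at 0.25 and 0.66273 at 0.35.
- UPM for 0.15-0.25: (0.39932 - 0.14085)/0.10 = 2.585
- UPM for 0.25-0.35: (0.66273 - 0.39932)/0.10 = 2.634

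The upper interval wins by 2.634/2.585 = 1.019, so the decision is D. Pr(p > 0.20) is 0.738, well short of anything that would make it DU.

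**Related cells.**

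| Cell | UPM 0.15-0.25 | UPM 0.25-0.35 | Computed | Printed |
|---|---|---|---|---|
| 1/4 | 2.024 | 2.044 | D | D |
| 2/7 | 2.162 | 2.507 | D | D |
| 2/8 | 2.585 | 2.634 | D | **S** |
| 2/9 | 2.946 | 2.640 | S | S |
| 3/9 | 1.742 | 2.620 | D | D |
| 3/12 | 2.977 | 3.060 | D | D |

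Over all 54 cells, 53 agree and only 2/8 departs. Treating 2/8 as a tie does not explain it: the tie at 1/4 is closer (2.044/2.024 = 1.010), and the table resolves that one to D.

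**Does another prior rescue the table?** I tried Beta(a,b) with a from 0.05 to 5 and b from 0.05 to 10 in steps of 0.05, which is 100 x 200 = 20,000 priors, with the same sub-intervals.
- None reproduces all 54 cells.
- None gives both D at 1/4 and S at 2/8.
- 101 miss exactly one cell: 2/8 for 95 of them and 1/4 for 6.
- Other common priors do worse: Beta(0.5,0.5) misses 6 cells, Beta(0.005,0.005) 11, Beta(0.2,0.8) 14 and Beta(2,2) 15.

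**Other partitions, uniform prior.** Dropping the short end intervals leaves 2/8 as the only mismatch. Merging them, or using width 0.05, adds a mismatch at 1/8 or 1/7 and still gives D at 2/8. The older three-interval mTPI misses 13 cells.

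**How likely is 2/8?** Section 4.1.1 requires that "at least 3 patients will be enrolled at each dose level", and section 9.1.2.1 says: "An estimated 24 to 30 evaluable patients may be enrolled in this part". With 8 dose levels the minimum is 8 x 3 = 24. One cohort of 8 makes 7 x 3 + 8 = 29; two make 6 x 3 + 2 x 8 = 34. So about one fits.

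The protocol does not define passing the preliminary assessment, so I took four versions. At a true DLT rate p = 0.20:

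| Assumed meaning of passing | Pr(pass) | Pr(pass and 2/8) | Pr(2/8 given pass) |
|---|---|---|---|
| 0/3, then at most 1/6 | 0.459 | 0.073 | 0.160 |
| 0/3 | 0.512 | 0.105 | 0.205 |
| At most 1/6 | 0.655 | 0.136 | 0.208 |
| At most 1/5 | 0.737 | 0.189 | 0.256 |

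For example, with at most 1/6 the joint probability is 0.8^6 x 0.2^2 + (6 x 0.2 x 0.8^5) x (2 x 0.2 x 0.8) = 0.0105 + 0.1258 = 0.136. For true rates from 15% to 35% the joint probability runs from 0.06 to 0.20 and the conditional from 0.10 to 0.39. These figures do not allow for the efficacy condition, or for the need to take a decision at exactly 8 patients.

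**The case against.** The strongest reply is that the decisive inputs are mine. The protocol fixes the target and the equivalence interval, but not the prior, the sub-intervals or the DU cutoff. Several points follow.

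- **DU labels.** If DU means Pr(p > 0.20) > 0.95, the uniform prior gives DU at 1/1 (0.960), where D is printed. If every DU label in rows 1 to 4 must also match at that cutoff, 17 of the one-mismatch priors remain: 11 with 2/8 odd and 6 with 1/4 odd. That is much closer than 95 to 6, and the uniform prior is not among the 17. However, the 0.95 is itself assumed, a cutoff between 0.960 and 0.9667 removes the 1/1 discrepancy, and a cohort of 1 is below the protocol's minimum of 3.
- **Partition.** The prior grid used one partition. With two equal intervals below 0.15, four equal intervals above 0.25 and a Beta(1,0.4) prior, D at 1/4 and S at 2/8 do occur together. That uses unequal widths, and 3/12 then departs.
- **Misreading.** A single misread letter cannot be wholly excluded in text taken from a PDF. Row 2 has the right number of entries and lines up with the worked example, so this is unlikely.
- **Consequence.** The cell sits on the edge of the interval, no DLTs were seen at dose levels 1 to 3, and the expansion dose has already been chosen.

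What stands is that 2/8 is the most plausible odd cell rather than a proven one, and that little depends on it in practice. What does not stand is that the table as printed follows from the named method: no setting tried reproduces all 54 cells.

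**Conclusion.** The point holds, as a minor one with medium confidence. Under a uniform prior and width-0.10 sub-intervals, which fit the other 53 cells, mTPI-2 gives De-escalate at 2/8 and Table 5 prints Stay. For every prior tried, at least one printed cell departs from the method, and 2/8 is the likeliest. On that reading the printed decision is the more permissive.

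The practical effect is small. The difference in unit mass is 1.9%, and Stay does not raise the dose. The next patient takes the cohort to 2/9 (S) or 3/9 (D), where table and calculation agree. The SRC may at any review "stay at the currently assigned dose level or whether the dose should be de-escalated to any lower dose". Nothing here shows that a patient was dosed wrongly.

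**What to change.** Change the 2/8 entry in Table 5 to D. If a non-uniform prior or a deliberate override was used, say so next to the table, and correct or document whichever cell then departs. Stating the prior, the sub-intervals and the DU cutoff would let a reader reproduce the table.

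The cost is one cell or one sentence. Amendment 5 already opens expansion at the highest tolerable dose from escalation, so the remaining work is mainly a check of SRC records for any cohort judged at exactly 2 DLTs in 8 patients, with a note in the CSR.
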